## 1 PRÉCIS

### 1.1 Study Title

A Clinician-Focused Nudging Intervention to Optimize Post-Surgical Prescribing

### 1.2 Objectives

Overall goal: Develop pilot data for a new, easily scalable strategy to optimize post-surgical opioid prescribing.

Specific objective #1: Evaluate feasibility and acceptability of carrying out a novel nudge intervention that may reduce excess postoperative opioid prescribing by surgeons.

Exploratory objective #2: Determine whether the nudge intervention leads to changes in subsequent postoperative opioid prescribing by surgeons.

Exploratory objective #3: Determine whether this technique affects patient opioid consumption, refill requests, medical visits for pain, satisfaction with analgesia, and opioid misuse.

### 1.3 Design and Outcomes

Pilot single site randomized controlled trial to assess the feasibility and acceptability of a nudging intervention providing surgeons with procedure-specific feedback regarding patients' postoperative opioid prescription-to-consumption ratio in individuals 18 years of age and older.

Primary outcomes:

*Feasibility:*

1. Percentage of surgeons approached who agree to participate in study
2. Percentage of patients contacted who agree to participate in study

*Acceptability:*

1. Surgeon-reported acceptability of intervention

Exploratory outcomes: Mean pre-post percentage change in procedure-specific prescription size, mean pre-post change in patient opioid consumption, opioid refills, medical visits for pain, satisfaction with analgesia, and opioid misuse, surgeon-reported perceived usefulness of intervention.

### 1.4 Interventions and Duration

In the first phase, patients undergoing specific elective surgeries at the study site (Vanderbilt University Medical Center [VUMC], Nashville, TN) during study days 1-60 will be contacted by telephone or electronically 14 days postoperatively (study days 15-74) and asked to perform an opioid pill count; they will also be asked about opioid refills, satisfaction with analgesia, emergency room visits or hospitalizations for pain, and opioid misuse.

First phase data will then be analyzed and patients' surgeons randomized in a 1:1 ratio to the intervention or control arms. After study day 97, surgeons in the intervention arm will be provided procedure-specific direct feedback on opioid prescribing and consumption for their patients who had surgery during days 1-60.

After this intervention, we will assess pre-post change in opioid prescription size (measured in oral morphine equivalents) from baseline between the two groups for surgeries performed during days 108-167

We will also contact patients undergoing post-intervention surgeries (during days 108-167) 14 days postoperatively (days 122-181) to assess pre-post changes in patient opioid consumption, satisfaction with analgesia, medical visits for pain, opioid refills, and opioid misuse.

## **1.5 Sample Size and Population**

**Patients (initial phase):** We anticipate successfully contacting 5 patients per day for a total of 300 patients.

**Surgeons:** We anticipate obtaining mean pre-post prescribing change in up to 60 surgeons (30 per group).

**Patients (second phase):** We anticipate successfully contacting 5 patients per day for a total of 300 patients.

### **3 STUDY OBJECTIVES**

#### **3.1 Primary Objective**

Evaluate the feasibility and acceptability of a novel nudge intervention that may reduce excess postoperative opioid prescribing by surgeons.

#### **3.2 Exploratory Objectives**

Determine whether surgeons randomized to the Intervention Arm will exhibit greater mean pre-post percentage change in procedure-specific prescription size compared to the Control Arm. Additionally, determine whether the novel nudge intervention affects patient opioid consumption, refill requests, medical visits for pain, satisfaction with analgesia, and opioid misuse.

### **4 BACKGROUND AND RATIONALE**

#### **4.1 Background on Condition, Disease, or Other Primary Study Focus**

Among those aged 55 and older, opioids caused 8,877 deaths in the U.S. in 2017 (the most recent year for which data are available). 4,564 of these deaths were from prescription opioids.(1) The total number of U.S. opioid-related deaths in 2017 was 47,600, 17,029 of which involved prescription opioids.

Physician prescribing is deeply connected with opioid use disorder: Most Americans misusing prescription opioids were either directly prescribed these medications or received them from a friend or relative with a prescription,(2) and most current heroin users started opioid use with prescribed medication.(3) Surgical prescribing comprises an increasing proportion of first-start opioid prescriptions to opioid-naïve patients;(4) 6% of such patients develop new persistent opioid use postoperatively.(5) Up to 70% of prescribed postoperative opioids go unconsumed and become a reservoir for potential diversion or misuse.(6)

#### **4.2 Study Rationale**

Evidence-based postoperative prescribing guidelines have been propagated(7-10) in order to decrease both the number of surgical patients developing new persistent opioid use and the overprescribing of post-surgical opioids. Other nudging techniques like changing electronic medical record prescription size defaults have been used in the surgical setting to decrease opioid prescribing,(11) although such tactics run the risk of increasing opioid prescribing for already-low prescribers.(12)

Despite these initiatives, evidence remains limited regarding the optimal methods for reducing post-surgical opioid prescribing.(13) Our proposed project will test a novel nudging technique that has not been studied in the postoperative opioid prescribing space: direct feedback to surgeons about their patients' opioid prescription-to-consumption ratios. Direct feedback to opioid prescribers after patients suffered a fatal opioid overdose has been shown to reduce subsequent opioid prescribing significantly.(14) We believe that providing granular data to a wide population of surgical prescribers (not just those whose patients overdose) will prove similarly effective. Should our intervention decrease

surgical prescribing, we anticipate it playing a significant role in the national strategy to combat the opioid crisis.

## 5 STUDY DESIGN

We plan a pilot randomized controlled trial randomizing surgeons to either intervention (direct feedback) or control (no direct feedback) arms. Surgeons frequently performing specific elective general, gynecologic, orthopedic, and neurological surgeries at VUMC will be identified during a 30-day study lead-in period. Then, patients aged at least 18 years undergoing these surgeries at VUMC during study days 1-60 will be contacted by telephone 14 days postoperatively (study days 15-74) and asked to perform an opioid pill count; they will also be asked about opioid refills, satisfaction with analgesia, emergency room visits or hospitalizations for pain, and opioid misuse. The electronic medical record will be also queried for the size of the initial postoperative opioid prescription as well as evidence of any refills for each enrolled subject. We anticipate successfully contacting 5 patients per day for a total of 300 patients in this initial phase. We plan to consent patients electronically at the time of the telephone contact as consenting patients immediately after surgery may influence their subsequent opioid consumption.

Surgeons will be consented without overt discussion of the nudge intervention. Following the first block of surgeries and associated patient follow-up (study days 1-74), data will be analyzed and then surgeons will be randomized in a 1:1 ratio to the intervention or control arms. Randomization will be stratified by both surgical specialty and by mean opioid prescription size during the initial block of surgeries. After study day 97, surgeons in the intervention arm will be provided procedure-specific direct feedback on opioid prescribing and consumption for their patients who had surgery during days 1-60.

After this intervention, we will assess pre-post change in opioid prescription size (measured in oral morphine equivalents) from baseline between the two groups for surgeries performed during days 108-167. That is, mean size of post-intervention prescriptions (from electronic medical record queries) will be compared with mean pre-intervention prescription size by the same surgeon for the same procedure in order to calculate change from baseline. Primary outcomes are measures of study feasibility and acceptability given that this is a pilot study. The main exploratory outcome will be mean percentage change in procedure-specific prescription size. We will then compare mean per-surgeon percentage change in prescription size between the direct feedback and no-direct-feedback groups. Multiple regression analyses adjusting for case type and surgical specialty will also be employed to permit more granular examination of the targeted changes. To evaluate other exploratory outcomes, we will contact patients undergoing post-intervention surgeries (during days 108-167) 14 days postoperatively (days 122-181) to assess pre-post changes in patient opioid consumption, satisfaction with analgesia, medical visits for pain, opioid refills, and opioid misuse. We again anticipate contacting 5 patients per day for a total of 300 patients in this second phase.

## 6 SELECTION AND ENROLLMENT OF PARTICIPANTS

## 6.1 Inclusion Criteria

Study *surgeon* participants must meet all the inclusion criteria below to participate in the study:

- General, gynecologic, orthopedic, or neurological surgeon at VUMC during the study period performing any of the surgeries listed below

Study *patient* participants must meet all the inclusion criteria below to participate in the study:

- Aged greater or equal to 18 years
- Undergoing specified elective general, gynecologic, orthopedic, and neurological surgeries at VUMC during the specified study periods (days 1-60 for the initial patient group; days 108-167 for the follow-up patient group)
  - General: laparoscopic or open cholecystectomy, laparoscopic or open appendectomy
  - Gynecologic: abdominal hysterectomy, laparoscopic/robotic hysterectomy, vaginal hysterectomy, anterior repair/colporrhaphy, posterior repair/colporrhaphy, tension-free vaginal tape procedure, sacrospinous ligament suspension, sacrocolpopexy, uterosacral ligament suspension, colpocleisis, perineorrhaphy
  - Orthopedic: total knee arthroplasty, total hip arthroplasty, total shoulder arthroplasty, 1- or 2-level spinal laminectomy and/or discectomy (without fusion)
  - Neurological: 1- or 2-level spinal laminectomy and/or discectomy (without fusion)
- Provided opioid prescription for postoperative pain relief (verified in VUMC EMR)
- Able to understand study procedures and participate in the pill count and telephone/electronic interview process in English or Spanish
- Provide informed consent

## 6.2 Exclusion Criteria

There are no planned exclusion criteria for study *surgeon* participants, although those performing <3 of the specified surgeries during the first 60-day period of surgeries will not be eligible for randomization.

Study *patient* candidates meeting any of the following exclusion criteria at baseline will be excluded from study participation:

- Opioid prescription filled (per VUMC electronic medical record [EMR] and patient self-report) between 3 months and 14 days prior to surgery
- Primary reason for surgery as assessed by chart review is cancer-related

- Surgery is a repeat/revision surgery (e.g., revision total knee arthroplasty)
- Patient has been inpatient for >3 days postoperatively prior to receiving post-discharge prescription
- Vulnerable populations: current pregnancy, prisoners
- Inability or unwillingness of patient to give informed consent
- (Partial exclusion) Prior participation in this study (e.g., a patient included in the initial patient group undergoing a left total knee arthroplasty on study day 15, followed by a right total knee arthroplasty on day 115; such a patient would be included in the initial patient group but would not be recontacted for the follow-up patient group)

### 6.3 Study Enrollment Procedures

During the 30-day lead-in period, study *surgeon* participants will be identified through VUMC EMR queries of historical and booked case numbers for the specific procedures listed in section 4.1, above. Given the nature of the planned behavioral nudging intervention, it is not feasible for full consent to be obtained prospectively from surgeon participants as this would very likely affect prescribing behavior in both the Intervention and Control Arms due to the Hawthorne effect. Consequently, we plan to request permission from the VUMC Institutional Review Board to utilize deception for *surgeon* participants, who will be asked to consent for participation in a study giving them information about their patients' opioid consumption (surgeons will be debriefed fully on study purposes upon completion of the study). Surgeon participants will be prospectively selected in a participant log kept by study staff. Surgeons will be randomized on a 1:1 basis to either the Intervention or Control Arms prior to administration of the nudge intervention. Enrolled surgeons must complete a minimum 3 listed cases during the initial 60-day study period (study days #1-60) to be eligible for randomization.

Study *patient* candidates will be identified through VUMC EMR queries of performed surgical cases for study surgeon participants. All patient candidates including procedures by study surgeons will be sent a pre-recruitment letter by the VUMC Department of Anesthesiology informing them that may be contacted by telephone postoperatively regarding the study. Study team members contacting patients will be blinded to the surgeon randomization assignments. All patient candidates undergoing included procedures by study surgeons and otherwise meeting inclusion/exclusion criteria will be contacted 14 days postoperatively by telephone or electronic messaging and asked to complete an opioid pill count and a brief verbal questionnaire relating to postoperative opioid use and analgesia. Because preoperative or immediate postoperative consenting for the study might affect patient participants' subsequent opioid consumption, we plan to obtain electronic informed consent from *patients* at the time of contact. Study research coordinators will securely document the consent process. Study personnel will also maintain a screening log containing records for all evaluated candidates as well as reasons for study ineligibility and non-participation of eligible candidates.

Additionally, at the request of the study Data and Safety Monitoring Board, a third participant population will comprise *all* patients undergoing surgery *of any kind* by

surgeons in the nudge intervention group for 60 days following receipt of the nudge intervention. This will entail only EHR queries on POD #10 and #30 (on a rolling basis) for pain-related medical concerns and healthcare visits. This is to determine whether surgeon prescribing practices changed sufficiently following nudge relief to compromise postoperative analgesia and potentially harm patients. These patients will not be contacted by study staff unless they otherwise meet inclusion criteria for the study as listed above.

## 7 STUDY INTERVENTIONS

### 7.1 Interventions, Administration, and Duration

The one-time contact of *patient* participants will take place on postoperative day 14 (or no later than postoperative day 19) for the initial contact group. After verifying eligibility and documenting consent, patients will be asked to obtain their prescribed opioid pill bottle and conduct a pill count. If the patient consumed the entirety of the prescription and disposed of the bottle, this will be documented. If the patient does not have their pill bottle readily available, arrangements will be made to follow up with the patient by telephone or secure electronic messaging later to complete this aspect of the query. Patient participants will also be asked to answer several questions related to our exploratory outcomes:

- Overall satisfaction with postoperative analgesia (numeric rating scale)
- To select from the following answers: “I received a) too many opioid pills, b) the right amount of opioid pills, c) too few opioid pills.”
- Whether patient required any medical visits primarily due to postoperative pain (office visits, emergency department visits, or hospital admissions)
- Whether additional opioid refills were prescribed after the initial postoperative prescription (this will also be evaluated through EMR queries)
- Evidence of opioid misuse (Current Opioid Misuse Measure-9 [COMM-9])

The one-time intervention for *surgeon* participants in the Intervention Arm will take place on approximately study day 97. This will entail procedure-specific direct feedback (through electronic communication) on patients’ opioid consumption-to-prescription ratio. E.g., “Your abdominal hysterectomy patients were prescribed a mean 60 opioid pills last month. These patients consumed a mean 20 pills (33%).” Surgeon participants who perform more than one of the specified procedures (see section 4.2, above) will receive nudging communications for each individual procedure. Since the data on opioid consumption provided to surgeons is based on self-report data from consented patients, surgeons will be specifically informed that the data is self-reported through inclusion of the following statement: “This is based off self-reported pill counts. The information is self-reported and not validated so it could be erroneous.”

Surgeon participants randomized to the Control Arm will not be contacted directly at any time during the study.

## **7.2 Handling of Study Interventions**

The one-time contact of *patient* candidates will take place as follows: (1) Initial contact of patients by research coordinators through telephone or secure electronic message; (2) consent process and electronic documentation of consent; (3) pill count and questionnaire by telephone or secure electronic message (REDCap Twilio).

The one-time intervention for *surgeon* participants in the Intervention Arm will be delivered by text message, paging or e-mail on the same day.

## **7.3 Concomitant Interventions**

### **7.3.1 Allowed Interventions**

All drugs and treatments/interventions are permitted.

### **7.3.2 Required Interventions**

There are no required interventions.

### **7.3.3 Prohibited Interventions**

There are no prohibited drugs and treatments/interventions.

## **7.4 Adherence Assessment**

No formal adherence assessment is planned.

# **8 STUDY PROCEDURES**

[figure not shown]
## **8.1 Schedule of Evaluations**

Assessment	Days -30 to 0	Days 1-60 Group #1 PT Surgeries	Days 15-74 Patient Phone calls	Day 75-93 Surgeon prescribing practice review	Day 97Surgeon Nudge Arm notification	Days 108- 167 Group #2 PT Surgeries	Days 122- 181 Patient Phone calls	Days 181+ Surgeon survey
Identification of Surgeon Participants	X							
Preliminary Screening of Patient Candidates (EMR/PDMP) – Initial Patient Group		X	X					
Inclusion/Exclusion Criteria – Initial Patient Group			X					
Consent of Patient Candidates – Initial Patient Group			X					
Pill Count – Initial Patient Group			X					
Exploratory Outcome Questions – Initial Patient Group			X					
Assessment of Pre-Intervention Opioid Prescribing by Surgeon Participants				X				
Randomization of Surgeon Participants				X				

[figure not shown]
Nudging Intervention					X			
Assessment of Post-Intervention Opioid Prescribing by Surgeon Participants						X	X	
Screening of Patient Candidates (EMR/PDMP) – Follow-Up Patient Group							X	
Inclusion/Exclusion Criteria – Follow-Up Patient Group							X	
Consent of Patient Candidates – Follow-Up Patient Group							X	
Pill Count – Follow-Up Patient Group							X	
Exploratory Outcome Questions – Follow-Up Patient Group							X	
Acceptability Questions - Surgeons								X
Adverse Events				X	X	X	X	X

## 8.2 Description of Evaluations

[figure not shown]
**Figure 1: Study Flow Diagram (Days -30 through 0)**

[figure not shown]
**Figure 2: Study Flow Diagram (Days 1 through 60)**

[figure not shown]
**Figure 3: Study Flow Diagram (Days 15 through 74)**

**Figure 4: Study Flow Diagram (Days 97 through 167)**

**Figure 5: Study Flow Diagram (122 through 181)**

### 8.2.1 Preliminary Evaluations (Days -30 to 0)

## Identification of Surgeon Participants

- Up to 60 general, gynecologic, orthopedic, and neurological surgeons at VUMC regularly performing the following procedures:
  - General: laparoscopic or open cholecystectomy, laparoscopic or open appendectomy
  - Gynecologic: abdominal hysterectomy, laparoscopic/robotic hysterectomy, vaginal hysterectomy, anterior repair/colporrhaphy, posterior repair/colporrhaphy, tension-free vaginal tape procedure, sacrospinous ligament suspension, sacrocolpopexy, uterosacral ligament suspension, colpocleisis, perineorrhaphy
  - Orthopedic: total knee arthroplasty, total hip arthroplasty, total shoulder arthroplasty, 1- or 2-level spinal laminectomy and/or discectomy (without fusion)
  - Neurological: 1- or 2-level spinal laminectomy and/or discectomy (without fusion)
- EMR query will be utilized to identify surgeons most frequently performing these surgeries historically at VUMC

- The date of screening and of enrollment of surgeon participants will be kept in the password-protected and encrypted research database.

Preliminary Screening of Patient Candidates (EMR/PDMP) – Initial Patient Group

- Age  $\geq 18$  years
- Undergoing specified surgeries with surgeon participants between study days 1-60
- Provided opioid prescription that was subsequently filled
- Opioid-naïve (no prior opioid prescriptions between study days -90 to -14)
- Non-cancer surgery
- Non-repeat/revision surgery
- Demographic information, including gender and race/ethnicity, will be collected
- Screening date will be recorded in the password-protected and encrypted research database

8.2.2 Initial Patient Group Contacts and Surgeon Pre-Intervention Prescribing Evaluation (Days 1-74)

Inclusion/Exclusion Criteria – Initial Patient Group

- Confirmation of inclusion/exclusion criteria first assessed during preliminary screening
- Assessment of other inclusion/exclusion criteria:
  - Able to understand study procedures and participate in pill count and interview process in English or Spanish
  - Not a member of a vulnerable population (current pregnancy, prisoners)
  - Able to give informed consent

Consent of Patient Candidates – Initial Patient Group

- Identified patient candidates will be contacted by telephone or electronically by trained research coordinators.
- After description of study is provided and risks reviewed, telephone or electronic consent will be obtained.
- Documentation of electronic consent and enrollment of patient participants will be made by the research coordinator and stored in the password-

protected, encrypted research database.

#### Pill Count – Initial Patient Group

- Consented patients will be asked to physically obtain their prescribed opioid pill bottle and conduct a pill count.
- Patients who report having consumed the entirety of their prescription and disposed of the bottle will be considered to have a pill count of 0; absence of the empty bottle will be documented in the patient's study record.
- For patients who consent to participate but do not have their pill bottle readily available, arrangements will be made to follow up with the patient by telephone or secure electronic messaging later to complete this aspect of the query.
- All data will be stored in a password-protected and encrypted research database.

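### The pill count makes no provision for leftover pills that have left the bottle, so the natural derivation books them as consumed or leaves the patient without a value

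*Combined protocol and SAP*

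**What the plan says.** Consumption is built from two inputs.

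- **Pills remaining.** Section 8.2.2 sets out a self-conducted count: "Consented patients will be asked to physically obtain their prescribed opioid pill bottle and conduct a pill count". Section 8.2.4 uses the same wording for the follow-up group, and 7.1 describes the same contact at about postoperative day 14, with day 19 as the limit for the initial group.
- **Prescription size.** Under section 5 the medical record will be "queried for the size of the initial postoperative opioid prescription as well as evidence of any refills for each enrolled subject". The quantity dispensed is not named as an input.

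Two rules cover a bottle that is not in the patient's hand. If it is gone: "Patients who report having consumed the entirety of their prescription and disposed of the bottle will be considered to have a pill count" of zero. If it is only not within reach, "arrangements will be made to follow up with the patient by telephone or secure electronic messaging later to complete this aspect of the query". Neither covers a patient who stopped early and no longer has the leftovers.

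The listed questions (7.1, 8.2.2, 8.2.4) cover satisfaction, whether the amount prescribed was right, medical visits for pain, refills and the COMM-9. None is described as giving a number of pills discarded, returned, lost or passed on.

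Screening in 8.2.1 and 8.2.4 requires "Provided opioid prescription that was subsequently filled", although 6.1 asks only that a prescription was provided. Section 11.4.2 lists consumption in oral morphine equivalents without a formula. The same counts supply the feedback ratio in 7.1 and 8.2.3.

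**The concern.** With these inputs, the obvious derivation is prescribed minus remaining. A pill that was neither taken nor still in the bottle then has nowhere to go except consumption. The same holds for a pill never dispensed after a partial fill. A patient who threw out both leftovers and bottle does not meet the only rule for a missing bottle, and later follow-up cannot count a bottle that no longer exists. That patient, a low consumer, has no value, while a full consumer without a bottle keeps one.

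Two uses of the number are at stake.

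- **The nudge.** It shows surgeons the gap between prescribing and use, and overstated use narrows that gap. Section 4.1 motivates the trial by saying that unused pills "go unconsumed and become a reservoir for potential diversion or misuse", yet a pill given away would be recorded as the patient's own use.
- **The exploratory consumption outcome.** The error grows with the number of leftover pills. If the nudge lowers prescription size in one arm, the error shrinks there and not in the other. That bears on the hypothesis in 11.1 of no between-arm difference in consumption.

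Patient contact is planned as a single occasion, so analysts could not reconstruct the missing quantity from the items listed.

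**Working it through.** **Inputs.** From the example message in 7.1 and 8.2.3: mean prescribed P = 60, mean consumed C = 20. The documents give no figure for pills that have left the bottle, partial fills or refill sizes, so every share below is an assumption.

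**Plan's own figure.** 20/60 = 33.3%, which reproduces the stated 33%.

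**1. Leftovers gone and booked as taken.** Let f be the share of unconsumed pills no longer in the bottle. Apparent consumption = C + f × (P − C) = 20 + f × 40.

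- f = 5%: 22 pills (37%)
- f = 10%: 24 pills (40%)
- f = 20%: 28 pills (47%)

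This applies only where the leftovers are gone but a count is still recorded, such as a kept bottle counted as empty or part-empty.

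**2. Leftovers and bottle both gone, no value.** Assume 10% of patients took all 60. For an overall mean of 20, the other 90% average (20 − 0.10 × 60)/0.90 = 15.56. If 20% of that group have no value, 18% of all patients drop out. Observed mean = (0.10 × 60 + 0.72 × 15.56)/0.82 = 17.2/0.82 = 21.0 pills (35%).

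**3. Partial fills.** If 10% received 30 of 60 pills, each adds 30 undispensed pills to apparent use: 20 + 0.10 × 30 = 23 pills (38%).

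**4. Carry-over into the pre-post outcome.** Hold true consumption at 20 and f constant. If mean prescription size falls from 60 to 40 in one arm, apparent consumption there changes by f × (40 − 60).

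- f = 5%: −1 pill
- f = 10%: −2 pills
- f = 20%: −4 pills

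An arm that stays at 60 shows no such change, so the whole amount appears as a between-arm difference.

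**5. Opposite direction.** If 10% of patients took a 20-pill refill that is not counted, consumption is understated by 0.10 × 20 = 2 pills. That would offset the f = 5% case in step 1 exactly.

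**The case against.** The case for leaving the plan alone has several parts.

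- **No formula credits every missing pill as consumed.** Correct. Section 11.4.2 gives none, and the zero rule depends on the patient reporting full consumption. Prescribed minus remaining is an inference, though the natural one from the inputs named. Section 12.2.3 refers to a Manual of Procedures that is not in the documents, so the point is limited to the items the protocol lists.
- **Missing bottles and unfilled prescriptions are handled.** Largely so. Bottles not at hand are followed up, and wholly unfilled prescriptions are screened out. What remains is bottles that are gone, and partial fills.
- **The larger figures mix two kinds of patient.** Step 1 needs a recorded count; a patient with neither leftovers nor bottle belongs in step 2, where the shift is about 1 pill. The two routes should be read separately, and both rest on assumed shares.
- **Net inflation is not shown.** This stands. Refills are asked about but not stated to enter consumption, and pills taken after the contact are not seen. A reader might infer that measured consumption is too high overall; the documents support only an upward component.
- **The consequences are modest.** The three primary outcomes in 11.4.1 do not use the count. Surgeons are told in 7.1 that the data are unvalidated self-report. Overstated use would weaken the nudge rather than push towards the under-prescribing named in 9.1. All this stands, but the caveat tells a surgeon neither the direction nor the size of the error.
- **A measure applied identically in both arms and periods cancels.** It does so only while prescription size stays the same, and the nudge aims to change prescription size.

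**Conclusion.** The gap is real and limited. The protocol lists no item for pills that left the bottle untaken, codes a discarded bottle only for full consumers, and does not define consumption. Under prescribed minus remaining, this component biases consumption upward by f × (P − C). In the protocol's example that means 22 to 28 pills instead of 20 for an assumed f of 5% to 20%; the missing-value route alone gives about 21. The between-arm effect depends on how far the nudge moves prescription size: 1 to 4 pills for an assumed fall from 60 to 40 over the same range of f.

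A stronger reading, that the trial's consumption data are inflated on balance or that its main conclusions are at risk, does not follow. Refill handling could offset the error, and feasibility and acceptability do not depend on the count. Prescription size, the main exploratory outcome, is read from the medical record rather than computed from the count. This is a cheap improvement that should be made before patient contacts begin.

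**What to change.** - **7.1, 8.2.2 and 8.2.4:** add one question on how many of the prescribed pills the patient did not take and no longer has (thrown away, returned, lost or given away). For a patient whose bottle is gone and who did not take everything, record the self-reported number taken and flag its source.
- **11.4.2:** define consumption as quantity dispensed (initial fill plus any refill up to the contact date, from EMR/PDMP), minus pills remaining from those fills, minus pills not taken by the patient, converted to oral morphine equivalents.
- **Nudge (7.1, 8.2.3):** use counts consistent with that definition, so that the prescribed and consumed figures cover the same fills.

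The cost is one question in a contact that section 10 expects to last 15 to 30 minutes in most cases, and one extra data field. This assumes that the EMR or PDMP, already used for screening and refills, shows the quantity dispensed. The drawback is one more self-reported number on a mildly sensitive subject.
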